## **Study Population**

Age of Participants: Women ages 18-35

#### Sample Size:

At Utah: 706 All Centers: Up to 850

#### **Inclusion Criteria:**

Eligible participants must be:

- 1. Between 18-35 years old
- 2. In need of EC (had unprotected intercourse within 120 hours 5 days)
- 3. Desire to prevent pregnancy for 1 year
- 4. Fluent in English and/or Spanish
- 5. Have a regular menstrual cycle (21-35 days)
- 6. Know their last menstrual period (+/-3 days)
- 7. Be willing to comply with the study requirements

8. Participants current preferred phone number must be functioning at the time of study entry and will be tested prior to enrollment

#### **Exclusion Criteria:**

1. Current pregnancy

2. Breastfeeding

3. Intrauterine infection within the past 3 months

4. Sterilization

5. Already have an IUD or contraceptive implant (Nexplanon) in place

6. Vaginal bleeding of unknown etiology

7. Known Gonorrhea or Chlamydia infection in the last 30 days (unless successfully treated at least 7 days prior to study entry)

8. Allergy to copper or Wilson's disease

9. Known abnormalities of the uterus that distort the uterine cavity

10. Use of oral emergency contraception within 5 days prior to enrollment

## Design

Prospective Biomedical Intervention or Experiment Randomized Trial

Both medications being studied in this trial are FDA approved and have undergone Phase 3 testing and extensive post-market surveillance. This study evaluates both of these medications for off label use as emergency contraceptives.

If enrollment goals are not being met (for example, <80 enrolled in the first 6 months or less than 10 participants per site at any time in the study when staff are available to enroll participants) and lack of willingness to be randomized is a stated barrier to participation, then we will introduce a PPC whereby participants who are interested in the study and eligible for participation but not willing to be randomized will be offered participation in a patient-preference cohort (PPC).

# **Study Procedures**

### Recruitment/Participant Identification Process:

Women who present for emergency contraception at Planned Parenthood clinics will be provided with an information sheet describing the two IUD options offered in this study. This will be provided to them by a member of the PPAU clinical staff. The information sheet also asks if they are interested in participating in a study where they would be randomized to one of the two IUDs offered in this study. They are also asked for age, ethnicity, site, and reason for declining participation. They are asked to mark Yes or No before giving the information sheet back to the clinical staff member. No identifiable information is collected on these participant information sheets and unless a woman agrees to screening for the study, she is not listed in a screening log.

Those women who mark yes are then approached either by the study coordinator or other IRB approved research staff for further screening and information on the study.

Note: Women who are under age 18 will be included in those who present for emergency contraception at Planned Parenthood clinics and complete the study information sheet. After a member of the research team reviews the initial eligibility criteria, these under age 18 women would be considered screen failures and would not be offered participation in the study.

Should the PPC be initiated, then potential participants interested in the study but who decline randomization will be offered participation in the PPC.

#### **Informed Consent:**

#### Description of location(s) where consent will be obtained:

Consent will be obtained in a private examination room at the clinic where the patient is receiving care.

#### **Description of the consent process(es), including the timing of consent:**

Due to the nature of this study, it may not be possible for patients to return at a later time to enroll in the study. Participants will have all questions answered prior to enrollment. The research staff are experienced in interviewing and working with this population. They will be certain to take the time needed to ensure that the patient understands the study and is consenting willingly. If the woman continues to have questions, she will be offered the opportunity to discuss the study in further detail with the PI or other medical providers with extensive experience with the clinical care of IUDs and emergency contraception.

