### PI Conflict of Interest Management Plan

The PI has met all requirements of the COI Management Plan, as follows:

I will provide annual reports of my compliance with this management plan to the Conflict of Interest Office for review.

I will disclose my financial conflict(s) of interest to the editors of all publications (journals, books, etc.) when submitting manuscripts or other reports of the results of this research. I will disclose my financial conflict(s) of interest in all public presentations of this research. The University of Utah will disclose my financial conflict(s) of interest on a publicly available web site. The publicly available disclosures will include my name, the name of the business entity(ies), the nature of the financial interest(s) and the dollar ranges or value of the financial interest(s) as available.

I will disclose my financial conflict(s) of interest in writing to all members of the research team. Members of the research team will be informed that if they have any concerns about my conflict(s) of interest, they can discuss those with the Individual Conflict of Interest Committee. I will disclose my financial conflict(s) of interest in writing to all subordinates working on this project. Subordinates will be informed that if they have any concerns about my financial conflict(s) of interest, they can discuss those with the department chair or the Individual Conflict of Interest Committee.

My evaluation of University subordinates will not be based, in whole or in part, on their participation (or refusal to participate) in non-University activities involving any business entity in which I have significant financial interest(s) as defined by the University Individual Financial Conflict of Interest Policy. The participation of subordinates in non-University activities involving such business entities will not be expected or required.

I will disclose my financial conflict(s) of interest in writing to all students working on this project. Students will be informed that if they have any concerns about my financial conflict(s) of interest, they can discuss those with their department chair, the chair of their graduate committee or the Individual Conflict of Interest Committee.

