My evaluation of University students will not be based, in whole or in part, on their participation (or refusal to participate) in non-University activities involving any business entity in which I have significant financial interest(s) as defined by the University's Individual Financial Conflict of Interest Policy. The participation of students in non-University activities involving such business entities will not be expected or required.

Publication of student, subordinate, or other investigator's work on the project will not be delayed beyond the standard University agreement for review of intellectual property issues. I will promptly disclose any and all new intellectual property arising from this research to the University of Utah Technology & Venture Commercialization.

I will identify a non-conflicted peer subject to the approval of the Individual Conflict of Interest Committee to review the research and results prior to publication.

I will disclose my financial conflict(s) of interest to all potential research participants in the informed consent documents.

A member of the research team who does not have any conflicts of interest related to this research or an appropriate third party will inform potential research participants of my financial conflict(s) of interest during the informed consent process.

I will recuse myself from participation in the process of obtaining informed consent from all potential research participants for this study. Informed consent for all potential research participants will be obtained by a member of the research team who does not have any conflicts of interest related to this research or by an appropriate third party approved by the Individual Conflict of Interest Committee.

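### The consent section lists the PI as someone who may discuss the study with women who still have questions, a route that the PI's own recusal rules out

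*Combined protocol and SAP*

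**What the plan says.** Two sections of the combined protocol and SAP bear on this.

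Under Informed Consent, the subsection headed "Description of the consent process(es), including the timing of consent" explains that women may be unable to come back later to enroll. It sets the rule that "Participants will have all questions answered prior to enrollment". Research staff are to make sure that the woman understands the study and agrees freely. If she still has questions, "she will be offered the opportunity to discuss the study in further detail with the PI or other medical providers". Those other providers are described as experienced in IUD and emergency contraception care. The sentence sets no condition about conflicts of interest for anyone it names.

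The PI Conflict of Interest Management Plan is written in the PI's voice and opens with "The PI has met all requirements of the COI Management Plan, as follows". Among its undertakings is: "I will recuse myself from participation in the process of obtaining informed consent from all potential research participants for this study". The next sentence says that consent "will be obtained by a member of the research team who does not have any conflicts of interest" related to the research, or by a third party approved by the conflict-of-interest committee. The plan also requires the conflict to be disclosed in the consent documents, and to be explained during the consent process by a non-conflicted team member or an appropriate third party.

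**The concern.** The recusal exists so that a person with a financial interest does not influence a woman's decision to join. The consent section names that same person as a possible source of further information for women who have not finished asking. These women are deciding at a visit to which they may not be able to return, and the decision is whether to accept randomization. One of the two arms is the LNG IUD alone for emergency contraception, which the section on research-only procedures says the clinics do not otherwise offer. Independent answers matter at this point.

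Staff who read only the consent section would see nothing against calling in the PI. If they did so, the PI would be taking part in a step that the management plan says the PI stays out of.

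**Working it through.** No figure in the plan depends on this and there is nothing to recompute. The check is a comparison of the two sections on four questions.

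1. **Is the discussion part of the consent process?** The document puts it there. It sits under the heading "Description of the consent process(es), including the timing of consent", directly after the duty to make sure that the woman understands and agrees freely.

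2. **Does it come before the decision is final?** Yes. The same paragraph requires that "Participants will have all questions answered prior to enrollment", and the further discussion is what is offered when questions remain.

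3. **How wide is the recusal?** The undertaking reads "I will recuse myself from participation in the process of obtaining informed consent from all potential research participants for this study". It covers participation in a process, which is wider than taking a signature, and it applies to all potential participants. The management plan also treats giving information as part of consent, because it specifies who must explain the PI's conflict during that process.

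4. **Is there an exemption?** None was found. No section limits the recusal to signing the form or allows the PI to answer questions before enrollment.

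Side by side:

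| Question | Consent section | Management plan |
|---|---|---|
| May the PI discuss the study with a woman before she enrolls? | Yes, as one named option | No, if the discussion is part of the consent process, where the document places it |
| To whom does it apply? | Any woman with remaining questions | All potential participants |
| Who else may act? | Other experienced providers, with no condition on conflicts | A non-conflicted team member or an approved third party obtains consent |

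The two sections are compatible only if the PI option is never used. An option that can never properly be used should not be listed.

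**The case against.** The strongest defence is that answering questions is not obtaining consent. On this reading, research staff obtain consent, the PI or another clinician only supplies clinical detail, and the sentence following the recusal confirms that its subject is who obtains consent. This reading is possible, but the wording of the recusal and the place of the discussion under the consent heading both tell against it. What stands is that a breach would be arguable rather than certain if the PI did speak to a woman.

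The second defence is that the PI is only one alternative. That is correct and it limits the point. A reader might infer that any site following the consent section must breach the management plan. The documents do not support that, because a site that always uses another provider complies with both.

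Third, the management plan contains other safeguards. The conflict is disclosed in the consent documents and explained by someone without a conflict, so a woman should know of it before any discussion with the PI. That reduces the harm. It does not replace recusal, since the plan requires both.

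Two further inferences should be resisted. A reader might conclude that the declaration "The PI has met all requirements of the COI Management Plan, as follows" is false. An option on paper does not show that the PI ever took part in a consent discussion, and nothing in the documents says so. A reader might also suspect that the other medical providers are conflicted. No section says that any of them is.

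**Conclusion.** The inconsistency is real and the consent section is wrong as written: it lists a route that the conflict-of-interest plan rules out. The conclusion rests on reading participation in the process of obtaining consent as including a discussion that the document itself places within that process. Nothing in the text points to a narrower meaning strongly enough to remove the conflict.

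The point is minor. It concerns participant protection and the document's consistency, and it does not bear on the margin, the sample size, the outcomes or the analysis. No count of affected women can be given. The documents do not say how many women have remaining questions or how often the PI would be the person called, and any number would rest on invented rates for both. Nor do the documents support a claim that consents already given are defective.

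**What to change.** In the consent-process subsection, delete the PI from the sentence on remaining questions. Direct those questions to medical providers experienced in IUD and emergency contraception care who have no conflict of interest related to this research. The condition on conflicts brings the sentence into line with the management plan and does not imply that any current provider has one.

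The cost is one edited sentence. No extra staff are needed, because the consent section already names other experienced providers and the management plan already requires that whoever obtains consent be free of conflict or be an approved third party. No change to the statistical sections follows.

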#### Procedures:

Women who meet inclusion/exclusion criteria will be offered participation in the randomization arm of the study. For those who agree, they will be randomized to either the copper IUD or the LNG IUD and the study procedures below will apply. All participants in the RCT will be informed to use a backup method of contraception (e.g. condoms) or sexual abstinence for the next 7 days to protect against unplanned pregnancy as women assigned to the LNG IUD will need this early protection. Providing this information to only women in the LNG IUD group could inform them of which device they received in the first month. This is a component of the treatment blinding. In the PPC only women selecting the LNG IDU will be informed to use a backup method as the copper IUD protects against future pregnancy risk immediately.

Should enrollment not meet expectations as previously described, then for those patients who meet all inclusion/exclusion criteria and wish to participate in the study, but do not agree to random assignment, we will offer them participation in a PPC. Participants in the PPC may

choose the IUD they desire. Once the participant decides which IUD they prefer, the study procedures below will apply.

### Enrollment (Initial Clinic Visit)

- Consent process
- Urine pregnancy test (Completed at the Planned Parenthood Clinic Lab)
- Assignment to either randomized arm or PPC arm
- IUD Insertion
- Data collection
- Diary instructions
- Gonorrhea/Chlamydia testing, if recommended per PPAU STI screening protocols

### 1 Month Follow-Up

- The 1 month follow-up appointment will be made on the day of enrollment. Urine pregnancy test and confirmation of IUD position will be conducted at the clinic. An IUD string check may also be performed.
  - Participants will be asked to complete a home pregnancy test on the day before their 1 month clinic visit that will be given to them at their enrollment visit. They will be asked to take a picture of the pregnancy test results and text the results picture to a dedicated Planned Parenthood clinic cell phone (number will be provided at the time of enrollment). This at-home testing will be confirmed at the in-clinic appointment as a proof-of-concept to establish this as a norm for future studies with the goal of reducing participant burden.
- The following information will also be obtained either at the 1 month follow-up appointment or by phone, text, or email link to an online data collection instrument for those participants not able to return to clinic for the 1 month follow-up.
  - Bleeding history
  - Sexual activity
  - Data collection including evaluation of satisfaction of method chosen, current use of contraception and review for potential adverse events
- If urine pregnancy test is positive, the following will occur:
  - Ultrasound and/or serum quantitative hCG pregnancy test as necessary to date the pregnancy (this will be completed at the Planned Parenthood Clinic Lab)
  - Removal of IUD
  - o Follow-up throughout remainder of pregnancy
  - Pregnancy options counseling and appropriate referral for pregnancy care based on desire to continue or terminate the pregnancy.

### 3, 6, and 9 months after enrollment

- Telephone, text, email links to online survey or completion with a research assistant by telephone, text, or email (based on participant preference)
- Review for potential adverse events

• Review of bleeding experience, questionnaire review including: unplanned pregnancy, abortion, sexual activity, IUD complications, contraception related side effects, participant clinic visits, use of condoms, employment status, income, school attendance and satisfaction with contraception method

### 12 months after enrollment (return visit)

- Urine pregnancy test (Completed at the Planned Parenthood Clinic Lab).
- IUD string check.
- Review for potential adverse events.
- Review of bleeding experience, questionnaire review including unplanned pregnancy, abortion, sexual activity, IUD complications, contraception related side effects, participant clinic visits, use of condoms, employment status, income, school attendance, and satisfaction with contraception method.
- If participant cannot come to the clinic for their for 12-month visit, they will be contacted by a research assistant for review of follow-up information (bullet point #4 above) which can be completed via telephone, text, or email links to an online survey (based on participant preference). The study team will also provide participants with a urine pregnancy test they can take at home (if unable to come into the clinic for this final visit) and ask that participants send the results of the home-urine pregnancy test to the study team via email, phone or text.

**\*\***Note: We have provided specifics about the questionnaires/surveys that will be asked of participants under each of the study procedure sections. It is our understanding that we are not required to submit full versions of the surveys to the IRB, as long as we have provided thorough descriptions of what will be asked of participants.

### PI Conflict of Interest Management Plan

The PI has met all requirements of the COI Management Plan, as follows:

I will provide annual reports of my compliance with this management plan to the Conflict of Interest Office for review.

I will disclose my financial conflict(s) of interest to the editors of all publications (journals, books, etc.) when submitting manuscripts or other reports of the results of this research. I will disclose my financial conflict(s) of interest in all public presentations of this research. The University of Utah will disclose my financial conflict(s) of interest on a publicly available web site. The publicly available disclosures will include my name, the name of the business entity(ies), the nature of the financial interest(s) and the dollar ranges or value of the financial interest(s) as available.

I will disclose my financial conflict(s) of interest in writing to all members of the research team. Members of the research team will be informed that if they have any concerns about my conflict(s) of interest, they can discuss those with the Individual Conflict of Interest Committee. I will disclose my financial conflict(s) of interest in writing to all subordinates working on this project. Subordinates will be informed that if they have any concerns about my financial conflict(s) of interest, they can discuss those with the department chair or the Individual Conflict of Interest Committee.

My evaluation of University subordinates will not be based, in whole or in part, on their participation (or refusal to participate) in non-University activities involving any business entity in which I have significant financial interest(s) as defined by the University Individual Financial Conflict of Interest Policy. The participation of subordinates in non-University activities involving such business entities will not be expected or required.

I will disclose my financial conflict(s) of interest in writing to all students working on this project. Students will be informed that if they have any concerns about my financial conflict(s) of interest, they can discuss those with their department chair, the chair of their graduate committee or the Individual Conflict of Interest Committee.

My evaluation of University students will not be based, in whole or in part, on their participation (or refusal to participate) in non-University activities involving any business entity in which I have significant financial interest(s) as defined by the University's Individual Financial Conflict of Interest Policy. The participation of students in non-University activities involving such business entities will not be expected or required.

Publication of student, subordinate, or other investigator's work on the project will not be delayed beyond the standard University agreement for review of intellectual property issues. I will promptly disclose any and all new intellectual property arising from this research to the University of Utah Technology & Venture Commercialization.

I will identify a non-conflicted peer subject to the approval of the Individual Conflict of Interest Committee to review the research and results prior to publication.

I will disclose my financial conflict(s) of interest to all potential research participants in the informed consent documents.

A member of the research team who does not have any conflicts of interest related to this research or an appropriate third party will inform potential research participants of my financial conflict(s) of interest during the informed consent process.

I will recuse myself from participation in the process of obtaining informed consent from all potential research participants for this study. Informed consent for all potential research participants will be obtained by a member of the research team who does not have any conflicts of interest related to this research or by an appropriate third party approved by the Individual Conflict of Interest Committee.

